## Schedule of Assessments

Study Procedures	Prior to treatment with the mouthpiece	5 mins after PEEP therapy	10 mins after PEEP therapy	15 mins after PEEP therapy	15 minutes of after cessation of PEEP therapy
Consent	X				
Oxygen saturation	X	X	X	X	X
Respiratory rate	X	X	X	X	X
Heart rate	X	X	X	X	X
Blood pressure	X	X	X	X	X
Work of breathing 	X	X	X	X	X
Arterial blood gases (if available)	X			X	
Adverse events	X	X	X	X	X

 presence of any of the following: stridor, grunting, nasal flaring, or accessory muscle use

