### **Requirements**

We are seeking a rapid evaluation of the safety, efficacy, and feasibility of the device in patients with COVID-19 and pulmonary compromise. In order to test the performance of the device, we would identify a cohort of patients with a diagnosis of COVID-19. This cohort would be

characterized as those who require supportive care with supplemental oxygen but for whom ventilator support is not yet indicated or available. Once the patient is identified, consents to the study, and progresses to meet inclusion criteria based on oxygen requirements (>6L NC), then baseline measurements of oxygen saturation, respiratory rate, heart rate, blood pressure and blood gas results (when available) would be recorded. Furthermore, perceived effort of respiration would be measured including stridor, grunting, nasal flaring, or accessory muscle use. Patients would then be given the GO2 PEEP MOUTHPIECE for use in conjunction with oxygen therapy. Metrics would be recorded prior to initiation of therapy, 5, 10 and 15 minutes after GO2 PEEP therapy and 15 minutes after cessation of therapy.

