### **Study Endpoints**

#### *Primary Endpoint*

Improved oxygen saturation by pulse oximetry after treatment with the GO2 PEEP MOUTHPIECE.

The secondary endpoints include:

1. Respiratory rate
2. Heart rate
3. Blood pressure
4. Subjective work of breathing
5. Arterial blood gases (if available)

Both primary and secondary endpoints will be used to evaluate the safety as well as the efficacy of the GO2 PEEP MOUTHPIECE.

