### **Study Procedures**

After an eligible COVID-19 patient on supplemental oxygen has been identified, the research coordinator will contact patient via HIPPA compliant communication technology. The study will be verbally explained in detail with the patient. At time of verbal consent, instruction on use of the device will be performed by research team. If the patient progresses to meet the inclusion criteria and is enrolled in the trial, baseline metrics as above will be recorded. Patients will be provided a GO2 mouthpiece to be used in conjunction with and oxygen delivery face mask set to deliver an equivalent FIO2 to their previous therapy. **All patients will be instructed to breathe slowly and deeply through the mouthpiece for 15 minutes total.** Metrics for primary and secondary endpoints will be recorded before and after use of the mouthpiece (immediately prior to use and then at 5, 10 and 15 minutes of use and then 15 minutes after cessation of use).

Any decline in patient condition will result in immediate removal of the GO2 PEEP MOUTHPIECE and further appropriate care by the critical care team.

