## Statistical Analysis Plan

As an emergent COVID-19 study, our goal is to examine the safety, feasibility and efficacy of adding the GO2 PEEP MOUTHPIECE to COVID-19 patients already on oxygen therapy.

We will assess safety, feasibility and efficacy by observation of changes in the primary and secondary endpoints. At the conclusion of the study, we will assess metrics before and after application of the GO2 PEEP MOUTHPIECE, but given the few number of patients and low power of this initial study, statistical significance is not the focus of the analysis. However, we plan to provide statistical summaries that would be useful in a possible subsequent study, such as overall efficacy of the device and patterns and trends in primary and secondary endpoints.

Summary statistics on oxygen saturation (primary endpoint) and respiratory rate, heart rate, blood pressure, subjective work of breathing, and arterial blood gases as available (secondary endpoints) will be reported at each measurement occasion for each patient.

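### Oxygen device, flow and FIO2 are not collected at any of the five readings, so a change in delivered oxygen could be mistaken for, or hide, a mouthpiece effect on saturation

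*Combined protocol and SAP*

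**What the plan says.** The primary endpoint is "Improved oxygen saturation by pulse oximetry after treatment with the GO2 PEEP MOUTHPIECE", with no minimum improvement and no reference to the oxygen being given. The Statistical Analysis Plan states: "We will assess safety, feasibility and efficacy by observation of changes in the primary and secondary endpoints". The Design section specifies a single arm, and Sample Size and Accrual gives 5 patients.

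Readings are taken "immediately prior to use and then at 5, 10 and 15 minutes of use and then 15 minutes after cessation of use" (Study Procedures). The Requirements section lists what is taken at the start: "baseline measurements of oxygen saturation, respiratory rate, heart rate, blood pressure and blood gas results (when available) would be recorded", plus perceived effort of breathing. The Schedule of Assessments repeats these items for each column up to "15 minutes of after cessation of PEEP therapy", with blood gases only before use and at 15 minutes.

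Oxygen dose appears in two places only. It is an entry threshold on nasal cannula (above 6 L in Requirements, at least 6 L in Inclusion Criteria). It is also a set-up instruction in Study Procedures: the mouthpiece is used with a face mask "set to deliver an equivalent FIO 2 to their previous therapy".

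**The concern.** Saturation and PaO2 both depend on the inspired oxygen at the moment they are read. Here the oxygen interface appears to change from cannula to mask when the mouthpiece starts, because no earlier switch is described. The plan gives no method for matching the two, no check of the match and no record of the result. It does not say that the setting is held through the 15 minutes of use and the 15 minutes after, or whether the last reading is taken on the mask or back on the cannula.

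At stake is what the before/after change can be said to mean. More delivered oxygen could look like benefit, and less could conceal a real benefit. Study Endpoints uses the same readings for safety, and a fall in saturation is on the adverse event list, so the ambiguity reaches the safety reading too. The SAP intends its summaries, including overall efficacy, to inform a possible later study, which would inherit it.

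**Working it through.** **Step 1: look for an oxygen reading in every list.**

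| Section | Items named | Oxygen device, flow or FIO2 collected? |
|---|---|---|
| Requirements | saturation, respiratory rate, heart rate, blood pressure, blood gases when available, effort of breathing | No (flow is an entry threshold only) |
| Study Endpoints | saturation; five secondary endpoints | No |
| Study Procedures | primary and secondary endpoint metrics at five times | No (one set-up instruction) |
| Schedule of Assessments | six rows at all five times, blood gases at two, consent at one | No |
| Statistical Analysis Plan | summaries of the same endpoints per patient and occasion | No |
| Adverse Events | worsening of the same measures, intolerance | No |
| Data Collection | data taken from the electronic medical record | Variables not listed |

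**Step 2: what each contrast contains.** In a single arm,

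observed change = mouthpiece effect + effect of any change in delivered oxygen + other effects of time.

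- Before use to 5, 10 or 15 minutes: the mouthpiece starts and the interface goes from cannula to mask.
- 15 minutes of use to 15 minutes after cessation: the mouthpiece stops, and the interface at the later reading is not stated.
- Before use to 15 minutes after cessation: same interface or different, not stated.

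Without the oxygen setting, the first two terms cannot be separated in any of the three. Blood gases do not help: they are optional, are taken at two of five times, and have no FIO2 beside them.

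**Step 3: how large the oxygen term could be.** The plan has no figure to reproduce. Everything below is assumed except the upper limit of starting saturation (92%, Inclusion Criteria). Assumed: starting saturation 88, 90 or 92%; starting FIO2 F = 0.44 or 0.60; unrecorded rise d = 0.05 or 0.10; and a standard empirical saturation curve with p = PaO2 in mmHg,

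S = 100 / (23400/(p³ + 150p) + 1).

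Inverting gives p = 54.7, 58.7 and 63.8 mmHg at S = 88, 90 and 92.

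*(a) PaO2 rises in proportion:* new p = p × (F + d)/F. Largest case, S = 88 and F = 0.44:
- d = 0.05: 54.67 × 0.49/0.44 = 60.9, S = 90.9, a rise of 2.9.
- d = 0.10: 54.67 × 0.54/0.44 = 67.1, S = 93.0, a rise of 5.0.

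Smallest case, S = 92 and F = 0.60, d = 0.05: 63.79 × 0.65/0.60 = 69.1, S = 93.6, a rise of 1.6.

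*(b) PaO2 rises half as much:* new p = p × (1 + 0.5d/F).

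*(c) Fixed shunt:* further assumptions are haemoglobin 12–14 g/dL, PaCO2 40 mmHg, constant arteriovenous difference, alveolar PO2 = 713F − 40/0.8, and oxygen content = 1.34 × Hb × S/100 + 0.003p. With the shunt fraction and the arteriovenous difference both fixed, arterial content rises by exactly the rise in end-capillary content. Example with Hb 12, S = 90, F = 0.44, d = 0.05:
- Alveolar PO2 goes from 263.7 to 299.4 mmHg, and end-capillary saturation from 99.87 to 99.91%.
- Content rises by 1.34 × 12 × 0.0004 + 0.003 × 35.65 = 0.006 + 0.107 = 0.113 mL/dL.
- In arterial blood that corresponds to a saturation rise of about 0.68 points.

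| Rise in FIO2 | (c) fixed shunt | (b) half-proportional | (a) proportional |
|---|---|---|---|
| 0.05 | about 0.6–0.7 | 0.8–1.6 | 1.6–2.9 |
| 0.10 | about 1.1–1.4 | 1.6–2.9 | 2.8–5.0 |

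Entries are percentage points of saturation, over all combinations of starting values.

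**The case against.** The strongest reply is that the plan already aims to hold oxygen equal: the mask is to match the earlier FIO2, so extra oxygen would be a departure from the plan. That stands as far as it goes. A reader might infer that a rise in saturation from more oxygen would be reported as efficacy. The documents support only that it could be. The instruction makes a difference less likely, but it states an intention at set-up, and nothing records whether it was met or maintained.

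A reader might also infer that such a change could never be detected afterwards. The documents do not support that. Data come from the medical record (Data Collection), the investigator watches through eICU during use (IRB Review and Informed Consent), and the Principal Investigator monitors each patient (Data Safety Monitoring Plan). Settings may be retrievable. What remains true is that the plan neither names them for collection nor ties them to the five readings.

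It is tempting, too, to picture staff turning up the oxygen during use. An obvious reason would be decline, and Study Procedures and Subject Safety both remove the mouthpiece on any decline. That narrows this route. The main exposure is then the cannula-to-mask match and the reading after cessation.

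The larger figures also need restraint. Proportional PaO2 is optimistic where shunt dominates, and Background and Significance describes PEEP as acting by reducing shunting. Finally, this is a limited safety and feasibility study of 5 patients, reported patient by patient, with significance not the focus. No test or threshold would be tipped. That lowers the stakes, but per-patient reporting is where an oxygen setting beside each saturation is most useful.

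**Conclusion.** The point holds as a gap in measurement. Oxygen device, flow and FIO2 are not named for collection at any reading, the interface appears to change as the mouthpiece starts, and there is no control arm. A change in delivered oxygen, up or down, could therefore be read as a mouthpiece effect or could mask one.

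The size cannot be derived from the documents. On the assumptions above, an FIO2 rise of 0.05 is worth about 0.6–0.7 points under fixed shunt and at most 2.9 under proportionality; a rise of 0.10 is worth about 1.1–1.4 and at most 5.0. The fixed-shunt figures are the safer guide, and the upper figures are limits, not expectations. Because the endpoint states no minimum improvement, even the smaller values could be read as improvement. The omission itself does not depend on any of these figures. The documents do not show that such a change will occur, only that the plan as written would not capture it.

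**What to change.** - **Schedule of Assessments:** add one row for oxygen device, set flow, and set or estimated FIO2, marked in all five columns. Add the same items to the metrics in Requirements and Study Procedures.
- **Statistical Analysis Plan:** report each saturation and each blood gas beside its oxygen setting. Flag any reading taken after a change in oxygen in either direction, and do not attribute the saturation change at a flagged reading to the mouthpiece alone. Say how the planned cannula-to-mask switch is treated, since flagging it as such would flag every reading during use.
- **Ratio:** report SpO2/FIO2 as supportive only, stating that FIO2 is an estimate across the switch. A flow meter shows flow, not inspired fraction, so the ratio carries the same unverified match and can look more precise than it is.

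The cost is a few more values at each time point and a few sentences in the SAP. Some readings may be flagged as not interpretable. Recording the setting will not prove that cannula and mask delivered the same FIO2, but it will show what was set and whether it moved. Oxygen management is unchanged.

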#### *Adverse Events*

Patients will be assessed for the following adverse events:

- Decreased oxygen saturation
- Increased respiratory rate
- Increased heart rate
- Low blood pressure
- Increased work of breathing
- Worsening arterial blood gases (if available)
- Patient unable to tolerate the mouthpiece

All serious adverse events will be assessed and reported per the Emory IRB Policies and Procedures.

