## **Data Safety Monitoring Plan**

With this very small, single-center, open label trial, there will not be a DSMB. However, the Principal Investigator will personally monitor each patient's use of the device. Therefore, there will be one-on-one physician monitoring, assessment and documentation for adverse effects and intolerance of device usage. If the subject experiences an adverse event as a result of the device, and the investigator staff believe it is in the best interest to discontinue study participation, the patient will be withdrawn. Any unanticipated or unforeseen complications will be reported by the investigator (or authorized designee) to the IRB.

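### As defined, work of breathing reads as one yes/no item over four signs, so through that item a patient with a sign at baseline cannot show worsening, and several signs cannot show partial improvement

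*Combined protocol and SAP*

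**What the plan says.** Work of breathing appears in four places in the combined protocol and SAP.

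- **Requirements:** "perceived effort of respiration would be measured including stridor, grunting, nasal flaring, or accessory muscle use". No scale is given.
- **Study Endpoints:** the fourth secondary endpoint is "Subjective work of breathing", again with no scale.
- **Schedule of Assessments:** the item is due at all five occasions. Footnote 1 defines it as "presence of any of the following: stridor, grunting, nasal flaring, or accessory muscle use".
- **Adverse Events:** the list includes "Increased work of breathing", with no threshold and no reference to footnote 1.

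On use of the endpoint, Study Endpoints states: "Both primary and secondary endpoints will be used to evaluate the safety as well as the efficacy of the GO2 PEEP MOUTHPIECE". The Statistical Analysis Plan adds: "We will assess safety, feasibility and efficacy by observation of changes in the primary and secondary endpoints". That section also promises summaries for each patient at each occasion, and it looks for trends that could inform a later study.

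On safety, the schedule gives adverse events their own row at all five occasions, and the Data Safety Monitoring Plan says "there will be one-on-one physician monitoring, assessment and documentation for adverse effects and intolerance of device usage". Study Procedures and Subject Safety both call for the mouthpiece to be removed if the patient's condition declines.

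**The concern.** Footnote 1 merges four signs into one item that is either present or absent. A patient who enters with accessory muscle use is already at the top of that item. If stridor and grunting then appear, the item does not change. A patient who goes from four signs to one does not change either.

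This matters because the endpoint is assessed through its changes, for benefit and for harm. Eligible patients have a saturation of 92% or less on at least 6 L by nasal cannula, so some may well show a sign at the start. With five patients, each one who cannot move on the item is a fifth of the data for this endpoint.

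A smaller issue is comparability. Baseline follows nasal cannula, whereas during use the patient has the mouthpiece and an "oxygen delivery face mask set to deliver an equivalent" inspired oxygen fraction, and the data are collected remotely. Footnote 1 has no entry for a sign that cannot be assessed.

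**Working it through.** The plan gives no figure for this endpoint to reproduce. There are two checks: what the item can register, and how many patients could be affected.

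**1. What the item can register**

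Input: four signs, each present or absent (footnote 1). That gives 2^4 = 16 patterns at baseline and 16 at follow-up, so 16 × 16 = 256 pairs.

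- Pairs with the same number of signs: 1² + 4² + 6² + 4² + 1² = 70.
- The other 186 split evenly by symmetry: 93 with more signs at follow-up and 93 with fewer.
- Worsening visible on a yes/no item: only from no signs to at least one, 1 × 15 = 15 pairs.
- Worsening that starts from at least one sign: 93 − 15 = 78 pairs (44 from one sign, 30 from two, 4 from three). The yes/no item shows 0 of them.
- Improvement visible on a yes/no item: only complete resolution, 15 pairs. Of the 78 partial improvements it shows 0.

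These are counts of possible patterns, not probabilities. By number of signs at baseline:

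| Signs at baseline | Upward steps, yes/no | Upward steps, count | Downward steps, yes/no | Downward steps, count |
|---|---|---|---|---|
| 0 | 1 | 4 | 0 | 0 |
| 1 | 0 | 3 | 1 | 1 |
| 2 | 0 | 2 | 1 | 2 |
| 3 | 0 | 1 | 1 | 3 |
| 4 | 0 | 0 | 1 | 4 |

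A patient with exactly one sign who loses it is visible either way. The loss on the improvement side needs two or more signs at baseline.

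**2. How many of the 5 patients could be affected**

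The documents give no prevalence for any sign. Assume a common prevalence p per sign and take two extremes of how the signs go together.

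- Independent signs: share with at least one sign = 1 − (1 − p)^4.
- Fully clustered signs (all or none): share = p.

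| Assumed p | Share, clustered | Of 5 | Share, independent | Of 5 |
|---|---|---|---|---|
| 0.1 | 10% | 0.5 | 1 − 0.9^4 = 34% | 1.7 |
| 0.2 | 20% | 1.0 | 1 − 0.8^4 = 59% | 3.0 |
| 0.3 | 30% | 1.5 | 1 − 0.7^4 = 76% | 3.8 |
| 0.4 | 40% | 2.0 | 1 − 0.6^4 = 87% | 4.4 |

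The chance that at least one of the 5 starts at the ceiling is 1 − (1 − share)^5. At a share of 10% this is 1 − 0.9^5 = 41%; at 40% it is 1 − 0.6^5 = 92%.

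**The case against.** The strongest objection concerns safety. A reader might infer that a patient with a sign at baseline can never be recorded as having the adverse event of increased work of breathing. The documents do not support that. The event is not tied to footnote 1, adverse events have their own row at every occasion, and a physician monitors each patient one-on-one. Someone who sees a patient go from one sign to three can record it. This part of the objection stands. What remains is that the physician has no stated standard for an increase when a sign is already present, and that this route does not restore the lost endpoint data.

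Second, footnote 1 states no scoring rule. It could be a list of signs to look for, and the wording in Requirements and Study Endpoints would allow sign-by-sign or subjective recording. The data form is not in the documents, so it may already have four boxes. That is fair, and it is why the point is about how the definition reads. It is nonetheless the only definition given, and its plain reading is any sign or none.

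Third, a reader might infer that the face mask biases the item towards benefit. This is not shown. Stridor and grunting are heard, and accessory muscle use is not on the masked part of the face, so hiding is plausible mainly for nasal flaring. Nothing says that an unseen sign is entered as absent, and a further assessment follows 15 minutes after the mouthpiece is out. Nor do the documents show that the patient is not asked about effort: they do not say whose perception is meant, and they provide two-way communication during use.

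Finally, this is one of five secondary endpoints in a descriptive pilot, and saturation, respiratory rate, heart rate and blood pressure also serve safety at every occasion. That limits the weight of the point but does not remove it.

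**Conclusion.** The point holds for the endpoint item. Read as written, footnote 1 shows none of the 78 worsening patterns that start with a sign and none of the 78 partial improvements. A sign count would show all 93 patterns in each direction. The plan relies on changes in this endpoint for safety and efficacy, so the information lost is information it says it will use.

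The share of patients affected is not known. Over an assumed prevalence of 10% to 40% per sign, it runs from 10% to 40% with full clustering and from 34% to 87% with independence, or about 0.5 to 4.4 of 5 patients. The higher range should not be quoted alone, since signs of respiratory distress plausibly occur together.

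The point does not extend to adverse event reporting as a whole, which can rest on physician judgement. The sample size and the descriptive analysis are unaffected. The change is worth making because it costs almost nothing.

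**What to change.** - At all five occasions, record each of the four signs separately as present, absent or not assessable. The last category is needed mainly for nasal flaring under the face mask.
- For each patient, report the individual signs and the 0 to 4 count with change from baseline, using only signs assessable at both times and stating how many those were.
- For the endpoint summary, call a count higher than baseline an increase, and list newly present signs beside it. Keep the two apart: a patient who loses three signs and gains one has a lower count but a new sign, and a rule that any new sign means worse would contradict the count.
- State that this summary does not replace the physician's judgement of adverse events.

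Renaming the endpoint to say that it consists of observed signs is optional.

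The cost is a few more tick boxes for signs the assessor already looks for. One limit remains: a patient with all four signs at baseline stays at the ceiling, because severity within a sign is not graded.

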## Statistical Analysis Plan

As an emergent COVID-19 study, our goal is to examine the safety, feasibility and efficacy of adding the GO2 PEEP MOUTHPIECE to COVID-19 patients already on oxygen therapy.

We will assess safety, feasibility and efficacy by observation of changes in the primary and secondary endpoints. At the conclusion of the study, we will assess metrics before and after application of the GO2 PEEP MOUTHPIECE, but given the few number of patients and low power of this initial study, statistical significance is not the focus of the analysis. However, we plan to provide statistical summaries that would be useful in a possible subsequent study, such as overall efficacy of the device and patterns and trends in primary and secondary endpoints.

Summary statistics on oxygen saturation (primary endpoint) and respiratory rate, heart rate, blood pressure, subjective work of breathing, and arterial blood gases as available (secondary endpoints) will be reported at each measurement occasion for each patient.

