## **Study Objective**

The objective of this study is to determine the safety, feasibility and efficacy of a bidirectional oxygenation PEEP mouthpiece in COVID-19 patients requiring supplemental oxygen.

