### **Deliverables and Timing**

This would serve as a limited safety and feasibility study to determine if further investigation is necessary. We estimate evaluation in 5 patients could be reached within one week. Thereafter, a more formal analysis could be performed as necessary.

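### Feasibility is to be judged from changes in vital signs, none of which measures completion of the 15-minute session, and five patients are said to be enough to establish it

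*Combined protocol and SAP*

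**What the plan says.** The Study Objective is to "determine the safety, feasibility and efficacy of a bidirectional oxygenation PEEP mouthpiece". Deliverables and Timing makes feasibility part of the decision on what follows: "This would serve as a limited safety and feasibility study to determine if further investigation is necessary".

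The only statement of how feasibility will be assessed is in the Statistical Analysis Plan: "We will assess safety, feasibility and efficacy by observation of changes in the primary and secondary endpoints". The results to be reported there, by patient and by time point, are "Summary statistics on oxygen saturation (primary endpoint) and respiratory rate, heart rate, blood pressure, subjective work of breathing, and arterial blood gases as available".

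Study Endpoints gives the same variables a narrower purpose: "Both primary and secondary endpoints will be used to evaluate the safety as well as the efficacy of the GO2 PEEP MOUTHPIECE". Feasibility is not named.

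The intended use of the device is in Study Procedures: "All patients will be instructed to breathe slowly and deeply through the mouthpiece for 15 minutes total". The same section allows a session to end early: "Any decline in patient condition will result in immediate removal of the GO2 PEEP MOUTHPIECE". Subject Safety repeats that rule. The Data Safety Monitoring Plan adds another route out: withdrawal after an adverse event caused by the device, where staff judge this to be best.

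Inability to tolerate the device is on the Adverse Events list, adverse events are assessed at every time point in the Schedule of Assessments, and the Data Safety Monitoring Plan has a physician document intolerance one-on-one.

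Sample Size and Accrual sets the number at 5 and asserts that this is enough to establish safety, feasibility and possible efficacy. The Statistical Analysis Plan is more cautious: "given the few number of patients and low power of this initial study, statistical significance is not the focus of the analysis".

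**The concern.** A feasibility result should say whether patients could use the device as intended. Here the intended use is one 15-minute session. A change in oxygen saturation or heart rate does not answer that question: a patient may improve and still take the mouthpiece out at 6 minutes, or complete the session with no change at all. Followed as written, the plan would draw its feasibility conclusion from the same measurements that serve safety and efficacy.

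The relevant observations are made, but the analysis plan does not say that they will be summarised. A later study would need two things for planning: how many patients completed the session, and why the others did not. The second matters because a session can end for several reasons, and a completion count alone does not separate them.

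The sample-size statement adds to this. It says five patients will settle feasibility when no criterion, target rate or precision is given.

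**Working it through.** **1. Does any endpoint measure completion?** The six variables in Study Endpoints (saturation, respiratory rate, heart rate, blood pressure, work of breathing, blood gases) are all physiological. None is time on the device or completion of the session. Study Endpoints assigns them to safety and efficacy; the Statistical Analysis Plan adds feasibility without adding a measure for it.

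**2. Are the missing data collected?** Largely yes. Intolerance is its own adverse-event item, adverse events are assessed at all five time points, and the session is watched one-on-one. The listed summaries contain neither adverse events, nor intolerance, nor completion. The gap is in the analysis plan, not in observation of the patient.

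**3. Can n = 5 be reproduced?** No. The documents give no confidence level, power, target rate or threshold, so the number cannot be derived or called arithmetically wrong. What can be checked is how much five patients can show.

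**4. What n = 5 supports.** Input from Sample Size and Accrual: n = 5. Assumptions: a two-sided 95% level, and the true rates used below. Exact (Clopper-Pearson) limits:

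- 5/5 complete: the lower limit solves p^5 = 0.025, so p = 0.025^(1/5) = 0.478. Interval 47.8% to 100%.
- 4/5 complete: the lower limit solves 5p^4(1 − p) + p^5 = 0.025, so p = 0.284; the upper limit solves 1 − p^5 = 0.025, so p = 0.995. Interval 28.4% to 99.5%.
- 0/5 intolerant: the upper limit is 1 − 0.025^(1/5) = 0.522. Interval 0% to 52.2%.
- 1/5 intolerant: interval 0.5% to 71.6%.

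Probability that all five complete, p^5, at an assumed true completion rate p:

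| p | P(5/5) |
|---|---|
| 60% | 7.8% |
| 70% | 16.8% |
| 80% | 32.8% |
| 90% | 59.0% |

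Probability of seeing at least one intolerant patient, 1 − (1 − q)^5, at an assumed true intolerance rate q: 41.0% at 10% and 67.2% at 20%. At a true rate of 10%, the study would more often than not see no intolerance.

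**5. Would a pass mark help?** Take a rule of at least 4 of 5 completing, with probability 5p^4(1 − p) + p^5. It is met 52.8% of the time at p = 70% and 18.8% at p = 50%. It separates those rates poorly, so none is proposed.

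**The case against.** The strongest reply is that little is lost. Results are reported for each patient at each time point, including 5, 10 and 15 minutes of use, so with five patients an early stop would often show as a break in the listing. Intolerance is captured as its own adverse event, and the plan's wording leaves room for other summaries. This stands in part. A reader might infer that early stops would be invisible or that intolerance data would be lost; the documents do not support either. But vital signs can still be taken after the mouthpiece is out, and a missing value carries no reason. The further summaries that the plan gives as examples concern efficacy and endpoint trends, not feasibility.

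A second reply is that the sample-size claim is tempered elsewhere: the plan concedes low power, calls the study limited, speaks only of possible efficacy, and leaves a more formal analysis for later. That is fair. A reader might infer that five patients is the wrong number. It is not an error for a pilot to have no power calculation. The fault is the strength of the claim.

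A third reply concerns reasons for stopping. It is tempting to set removals for worsening aside as the course of COVID-19. The documents do not support that. With a single arm and a breathing device, worsening during use could come from either the disease or the device, and the Data Safety Monitoring Plan expressly foresees adverse events caused by the device. Reasons can also overlap: a patient who cannot tolerate the mouthpiece because breathing has become harder meets two listed adverse events.

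Finally, completion is not the only possible aspect of feasibility; accrual within a week and remote consent and data collection are others. These could be reported as well, but they do not replace a measure of device use.

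**Conclusion.** The point holds as a fault in the analysis plan that should be corrected. Feasibility is an objective and part of the basis for further work, yet the stated rule assesses it with measures that do not show whether patients completed the session. Intolerance and adverse events are recorded but have no place in the listed summaries.

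The claim that five patients will establish safety and feasibility is not supported. The best possible completion result leaves a lower limit of 47.8%, and the best possible intolerance result an upper limit of 52.2%. These figures rest on an assumed 95% level. With no threshold in the documents, they do not show that the device is infeasible, nor that five of five would be a poor result; they show how wide the uncertainty remains.

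The finding does not invalidate the study or its physiological summaries.

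**What to change.** **Statistical Analysis Plan and Study Endpoints.** Assess feasibility by the number of enrolled patients who complete the 15-minute session, out of all enrolled. All enrolled is the right denominator because, under Protection of Human Subjects, the mouthpiece is delivered after enrolment. Keep the physiological changes for safety and efficacy.

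**Listed summaries.** Add counts of adverse events, and counts of reasons for not completing:

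- intolerance
- removal for worsening (Study Procedures, Subject Safety)
- withdrawal for a device-related adverse event (Data Safety Monitoring Plan)
- never started
- other

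Allow more than one reason per patient, and state that worsening during use is not presumed to be either disease course or device effect. Give exact 95% intervals for completion and intolerance as description only, with no pass mark.

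**Sample Size and Accrual.** Say that five patients will give a preliminary description of safety, feasibility and possible efficacy, in place of the present claim of sufficiency.

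**Cost.** Wording changes in three sections and two fields in the study spreadsheet: session completed (yes/no), and reason or reasons if not. The session is already monitored, so no new patient assessment is needed, and the rule for removing the device is unchanged. The downside is that the intervals are wide at n = 5.
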